6.2. Study procedures

Patients in participating centers are screened on a daily basis. Eligible patients are included during the 28–day observation period, from Monday at 8:00 AM to the Monday four weeks later at 7:59 AM (in time zones of the participating centers). The timing of the 28–day observation period will be flexible for participating centers and determined at a later stage together with the international study–coordinator and each national investigator. Times points of data collection:

- Demographic and baseline data are collected from the clinical files – at ICU admission;
- Types, quantities, of administered fluids– during the first three calendar days with high-granularity. From day 4-7 lower granularity data concerning the total volume of infused fluids will be collected;
- Types and modalities of administration of vasopressors – over a maximum of seven days of ICU admission;
- Vital signs, laboratory results and limited treatment parameters are collected – once daily for a maximum of seven days;
- Cumulative fluid balance – calculated once a day on a time point convenient per each center for a maximum of seven days; and
- Outcomes – recorded at 90 days, the day of death or hospital discharge, whichever comes first.

6.2.1. Inclusion

During a 28–day period, all admitted patients are screened daily by a local investigator. To reduce workload in high-volume ICU’s, local investigators can opt to stop study screening and enrollment after every 20 participants. However, once committed to a 20-participant block, researchers must continue until its completion before reassessing.

6.2.2. Collection of data

Data is collected from the patient medical chart, unless a local electronic system to register data can be used (e.g., patient data management system). Local investigators transcribe the collected data onto an Internet–based electronic CRF (Castor Electronic Data Capture). Access to the data–entry system is protected by a personalized username and password.

6.2.3. Data to be collected

The following data will be collected for all enrolled patients admitted to ICU during the screening period. Day 0 is defined as the day of initiation of invasive ventilation. Day 1 is defined as the first full calendar day after initiation of invasive ventilation. In patients that are not invasively ventilated at ICU admission day -3 to -1 are defined as the days before intubation but after ICU admission.

A. At ICU admission;

- Gender, male/female/other;
- Age, years;
- Weight, kg;
- Length, cm;
- Ethnicity, Black, East Asian, Indigenous (First Nations, Inuk/Inuit, Métis), Latin American, Middle Eastern, South Asian, Southeast Asian, White;
- Reason for ICU admission;
- Traumatic brain injury?;
- Sub-arachnoid hemorrhage?
- Date of ICU admission;
- Date of start of invasive ventilation;
- Did the patient receive non-invasive ventilation or high-flow nasal oxygen prior to intubation, if so: on which day?;
- Serum creatinine, $\mu\text{mol/L}$ or mg/dL , lowest in the last year, if available; and
- If the reason for ICU admission was burns: what was the cause of the burn and how much total body surface area is affected by the burns
- If the reason for ICU admission was sepsis, what was the focus of the sepsis (e.g. respiratory, abdominal)

B. On day 0;

- Type and volume, ml, of each fluid infusion (including medication and parenteral nutrition);
- Type and volume of oral fluids;
- Anuria ≥ 12 hours?, yes/no;
- Urine output, ml, over 24 hours;
- Extracorporeal life support, venoarterial/venovenous/no;

- Renal replacement therapy, yes/no, if yes;
 - Volume extracted by ultrafiltration, ml, over 24 hours;
- Cumulative fluid balance, ml;
- Loop diuretics given, yes/no, if yes;
 - Furosemide, yes/no, if yes;
 - (if no furosemide used) Bumetanide, yes/no, if yes;
 - (if no bumetanide or furosemide used) Torasemide, yes/no, if yes;
 - (if no Torasemide, bumetanide, furosemide used) Edecrin, yes/no;
- Additional diuretic given (thiazide, carbonic anhydrase inhibitor or mineralocorticoid antagonist), yes/no;
- Serum creatinine, $\mu\text{mol/L}$ or mg/dL , at a convenient fixed time point;
- Serum hemoglobin, $\mu\text{mol/L}$ or mg/dL , at a convenient fixed time point;
- Serum albumin, at a convenient fixed time point;
- Vasopressors initiated, yes/no, if yes;
 - Time between ICU admission and initiation of vasopressors, hours;
 - Drug(s) used as vasopressor;
- Mean arterial pressure (MAP) mmHg, at a convenient fixed time point;
- Heart rate, beats/min, at a convenient fixed time point;
- Atrial fibrillation or flutter during the last day, yes/no;
- Arterial or venous lactate, if measured, mmol/L , highest and lowest value;
- (Central) venous oxygen saturation ($S(c)VO_2$), mmol/L , if measured, highest and lowest value;
- Arterial partial pressure of oxygen (PaO_2), kPa or mmHg , at a convenient fixed time point;
 - (if no PaO_2 is known) Peripheral arterial oxygen saturation (SpO_2), percentage, at a convenient fixed time point;
- Inspired oxygen fraction, %, at time of PaO_2 or (if no PaO_2 is known) SpO_2 ;
- Suspected or confirmed infection that causes organ dysfunction (sepsis) yes/no;
- Was there new-onset (<7 days) respiratory symptoms, or acute worsening of respiratory symptoms?, yes/no, if yes;
- Are there bilateral opacities on chest imaging (including lung ultrasound), yes/no;
- If there was hypoxemia, was the hypoxemia explained by cardiac failure, yes/no?

- Richmond Agitation Sedation Scale (RASS), highest value of this day after intubation; and
- Sequential Organ Failure Assessment (SOFA) score.

C. Daily on day 1 and day 2;

- Type, volume, ml, and rate, ml/min, of each separate fluid infusion (including medication and parenteral nutrition);
- Type and volume of oral fluids;
- Anuria \geq 12 hours?, yes/no;
- Urine output, ml, over 24 hours;
- Extracorporeal life support, venoarterial/venovenous/no;
- Renal replacement therapy, yes/no, if yes;
 - Volume extracted by ultrafiltration, ml, over 24 hours;
- Cumulative fluid balance, ml;
- Loop diuretics given, yes/no, if yes;
 - Furosemide, yes/no, if no;
 - (if no furosemide used) Bumetanide, yes/no, if no;
 - (if no bumetanide or furosemide used) Torasemide, yes/no;
 - (if no Torasemide, bumetanide, furosemide used) Edecrin, yes/no;
 - Additional diuretic given (thiazide, carbonic anhydrase inhibitor or mineralocorticoid antagonist), yes/no;
- Serum creatinine, $\mu\text{mol/L}$ or mg/dL , at a convenient fixed time point;
- Serum hemoglobin, $\mu\text{mol/L}$ or mg/dL , at a convenient fixed time point;
- Serum albumin, at a convenient fixed time point;
- Vasopressors given, yes/no, if yes;
 - Time between ICU admission and initiation of vasopressors, only if not initiated on day 0, hours;
 - Drug(s) used as vasopressor;
- MAP, mmHg, at a convenient fixed time point;
- Heart rate, beats/min, at a convenient fixed time point;
- Atrial fibrillation or flutter during the last day, yes/no;
- Arterial or venous lactate, mmol/L , at a convenient fixed time point;
- Serum sodium, mmol/l , at a convenient fixed time point;

- Serum chloride, mmol/l, at a convenient fixed time point;
-
- S(c)VO₂, mmol/L, highest and lowest value;
- PaO₂, kPa or mmHg, at a convenient fixed time point;
- (if no PaO₂ is known) Peripheral arterial oxygen saturation (SpO₂), percentage, at a convenient fixed time point;
- Inspired oxygen fraction, %, at time of PaO₂ or (if no PaO₂ is known) SpO₂;
- Was there new-onset (<7 days) respiratory symptoms, or acute worsening of respiratory symptoms?, yes/no, if yes;
- Are there bilateral opacities on chest imaging (including lung ultrasound), yes/no;
- If there was hypoxemia, was the hypoxemia explained by cardiac failure, yes/no?
- Richmond Agitation Sedation Scale (RASS), highest value of the day; and
- SOFA score.

D. Daily on day 3 to 7 or ICU discharge; and on day -1, day -2 and day -3;

- Total volume of infused fluid, ml, over 24 hours
- Cumulative fluid balance, ml, over 24 hours;
- Urine output, ml, over 24 hours;
- Extracorporeal life support, venoarterial/venovenous/no;
- Renal replacement therapy, yes/no, if yes;
 - Volume extracted by ultrafiltration, ml, over 24 hours;
- Loop diuretics given, yes/no, if yes;
 - Furosemide, yes/no, if no;
 - (if no furosemide used) Bumetanide, yes/no, if no;
 - (if no bumetanide or furosemide used) Torasemide, yes/no;
 - (if no Torasemide, bumetanide, furosemide used) Edecrin, yes/no;
 - Additional diuretic given (thiazide, carbonic anhydrase inhibitor or mineralocorticoid antagonist), yes/no;
- Serum creatinine, µmol/L or mg/dL, at a convenient fixed time point;
- Serum hemoglobin, µmol/L or mg/dL, at a convenient fixed time point;
- Serum albumin, at a convenient fixed time point;
- Vasopressors used, yes/no, if yes;
 - Drug(s) used as vasopressor;

- MAP, mmHg, at a convenient fixed time point;
- Heart rate, beats/min, at a convenient fixed time point
- Atrial fibrillation or flutter during the last day, yes/no;
- Arterial or venous lactate, mmol/L, at a convenient fixed time point;
- Serum sodium, mmol/l, at a convenient fixed time point;
- Serum chloride, mmol/l, at a convenient fixed time point;
- PaO₂, kPa or mmHg, at a convenient fixed time point;
- (if no PaO₂ is known)) Peripheral arterial oxygen saturation (SpO₂), percentage, at a convenient fixed time point;
- Inspired oxygen fraction, %, at time of PaO₂ or (if no PaO₂ is known) SpO₂; and
- SOFA score.

E. Events (at day 7 or ICU discharge, whichever comes first)

- Were vasopressors initiated before ICU admission?, yes/no;
 - If no: Date of initiation of vasopressors after ICU admission, date;
- Route of initiation of vasopressors, central venous/peripheral venous;
- Did the patient develop AKI; yes/no;
 - if yes, on which study day?, day;
- Did the patient develop rhabdomyolysis; yes/no;
 - if yes, on which study day?, day;
- If the patient was admitted for sepsis, what was the suspected or proven pathogen causing the sepsis?

F. Follow-up (at hospital discharge, day 90, or death, whichever comes first)

- Vital status, alive/dead, if dead;
- Date of death;
- Reintubation, yes/no, if yes;
 - Number of reintubations;
 - Date of initial extubation;
 - Date of reintubation;
- Date of last extubation (or in the case of tracheostomy 24 hours without support from the ventilator);
- Date of ICU discharge;

- Date of hospital discharge; and
- Subjects requires renal replacement therapy or hemodialysis, yes/no.

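### The day-0 vasopressor item asks about starts, not use, so a vasopressor already running when ventilation begins, and its drug, can go unrecorded that day

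*Protocol*

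**What the plan says.** All item wording below is from Protocol section 6.2.3, which fixes the time axis by ventilation and not by ICU admission: "Day 0 is defined as the day of initiation of invasive ventilation".

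- List B (day 0): "Vasopressors initiated, yes/no, if yes". Two sub-items depend on a yes: "Time between ICU admission and initiation of vasopressors, hours" and "Drug(s) used as vasopressor".
- List C (days 1 and 2): "Vasopressors given, yes/no, if yes", with the drug under a yes. The time from ICU admission to the start is requested only where the start was not on day 0.
- List D (days 3 to 7, and days −3 to −1): "Vasopressors used, yes/no, if yes", with the drug under a yes and no start-time item.
- List E (day 7 or ICU discharge): "Were vasopressors initiated before ICU admission?, yes/no". If not, the start date is requested. Route is also recorded, but not the drug.

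Elsewhere, section 5.1 says that vasopressor use is among the data recorded each day once ventilation begins. Section 6.2 plans to collect "Types and modalities of administration of vasopressors" for up to seven days of the ICU stay. Section 6.1.2 lists vasopressor types as a secondary parameter, and the Summary adds duration of continuous vasopressor administration.

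**The concern.** One daily variable changes meaning on one day. On every other study day the item records exposure. On day 0 it records a new start, and the drug is captured only if that start occurred.

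The affected patients are ones the protocol itself expects. Section 5.2 allows ventilation to begin up to 3 days after ICU admission, list D collects vasopressor data on the ICU days before intubation, and list E asks about starts before the ICU. Such a patient can reach day 0 with a vasopressor already running.

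At stake is the daily record behind two secondary outcomes, vasopressor type and duration. No stop date or stop time is listed anywhere in section 6.2.3, so the day-by-day answers are the only listed source for duration. The same record may also feed the outcome associations named among the aims in section 3.1.

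**Working it through.** The protocol states no figure on this point, so the check compares the lists.

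**Step 1: which reading fits the text better.** List C asks for the start time only where the start was not on day 0, which treats the day-0 item as a start on that day. Within list B, loop diuretics are asked about as given, so the drafters had a word for exposure and used another for vasopressors. Both favour the plain reading, a new start on day 0. The looser reading is started by day 0.

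**Step 2: what each kind of patient produces.**

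| Patient | List D, days −3 to −1 | List B, day 0, plain reading | List B, day 0, looser reading | List E |
|---|---|---|---|---|
| (a) Started on day 0 | no, or no such days | yes, drug named | yes, drug named | start date |
| (b) Started on days −3 to −1, running on day 0 | yes, drug named | **no, no drug** | yes, drug named | start date |
| (c) Started before the ICU, running on day 0 | yes, drug named, if such days exist | **no, no drug** | yes, drug named | pre-ICU start |
| (d) Never treated | no, or no such days | no | no | no start |

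On the plain reading, (b), (c) and (d) have the same day-0 entry, although (b) and (c) are users that day. On the looser reading they separate, but the time sub-item would be negative for (c).

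**Step 3: what the other lists can restore.** Inclusion requires more than 24 hours of ventilation, so a day-1 entry should exist.

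- Day −1 yes and day 1 yes: day-0 use can be inferred. The drug can be inferred only if both days name the same one.
- Pre-ICU start, no day −1, day 1 yes: day-0 use can be inferred. The drug has to be assumed to be that of day 1.
- Earlier start, day 1 no: the vasopressor items do not show whether it was still running on day 0.
- Pre-ICU start, ventilated on the admission day, stopped that day: days 0 and 1 are both no, there are no earlier ICU days, and no vasopressor item names the drug.

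**Step 4: effect on duration.** Take a patient treated on days −1, 0 and 1. True days of use are 1 + 1 + 1 = 3. The plain reading records 1 + 0 + 1 = 2 and looks like a stop and a restart.

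**Step 5: size.** If every site used the plain reading and no lists were combined, recorded day-0 use = true day-0 use × (1 − c), where c is the share of day-0 users who started earlier. The protocol gives neither term, so no figure follows.

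**The case against.** The wording admits another reading. The day-0 sub-item counts hours from ICU admission, which makes sense for any start up to and including day 0. List D has no start-time item, so the looser reading would give starts on days −3 to −1 a place for their hour. The clause in list C can also mean that the time has not already been entered. This much stands: one cannot say that every carried-over patient will be entered as a non-user. But if sites split between readings, the same entry means different things across an expected minimum of 200 ICUs in 30 countries, and that is still a fault of the item.

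Much of the information also sits elsewhere, as step 3 shows. In addition, the day-0 fluid item covers medication infusions and may catch a vasopressor, though it is unclear whether type there means the drug or the carrier fluid. SOFA is listed only as a score. This too largely stands for day-0 use; it stands less well for the day-0 drug.

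The eCRF screens are not shown, and help text there may settle the meaning. That is possible, but the protocol list should still agree with sections 5.1 and 6.2.

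A reader might go further and infer a large undercount on day 0, or a biased comparison of low- and middle-income with high-income countries. The documents support neither. They give no share of patients already on a vasopressor, so any percentage would only multiply assumed inputs. They specify no day-0 comparison between country groups, and section 8.2 leaves the details of each analysis to separate plans. Nor do they say that confounding by shock peaks on day 0.

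**Conclusion.** The point holds as a data-capture fault. Day 0 is the one day without a question on vasopressor use, contrary to the stated intention in section 5.1. Followed as written, list B does not directly record use or drug for patients whose vasopressor was started earlier and is still running; read loosely, it does, and sites may then be inconsistent.

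The consequence is limited. Day-0 use can often be rebuilt from lists C, D and E. What remains is the day-0 drug, most clearly in pre-ICU starters with no day −1 record whose drug is stopped or changed on day 0, together with a weaker basis for duration. The number affected cannot be stated from the documents. Start date and route come from list E and are unaffected, as are the primary fluid parameter and the sample size. The conclusion rests on the protocol's item list being what sites see or what the eCRF was built from.

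**What to change.** In list B, replace the present item with *Vasopressors given on day 0, yes/no*, and nest the drug(s) under it as on days 1–7. Add *first started on day 0, yes/no*, with the time from ICU admission asked only if yes. Using the same verb in lists B, C and D would remove any remaining doubt.

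The cost is one reworded item and one extra tick box, from the same chart and with no extra patients. One limit should be accepted knowingly: list B would then not hold the hour of a start on days −3 to −1. List E still gives its date, and list C's time item, read literally, would apply if the vasopressor is still given on day 1.

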3.2. Hypotheses

There is large variation in fluid and vasopressor therapy in critically ill invasively ventilated patients (primary); there are differences in fluid and vasopressor therapy between LMICs and HICs; certain aspects of fluid and vasopressor therapy have an independent association with clinical outcomes.

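### Day-0 physiology is read at a convenient fixed hour with no clock times, so for patients ventilated at ICU admission its order relative to early vasopressors and fluids cannot be recovered

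*Protocol*

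**What the plan says.** Protocol Section 6.2.3 sets the time axis: "Day 0 is defined as the day of initiation of invasive ventilation", and day 1 is the next full calendar day.

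- **Day-0 physiology (list B).** The items include "Mean arterial pressure (MAP) mmHg, at a convenient fixed time point", "Heart rate, beats/min, at a convenient fixed time point" and "Serum albumin, at a convenient fixed time point". Creatinine, haemoglobin and PaO2 (or SpO2 where there is no PaO2) carry the same timing wording. FiO2 follows the oxygenation reading: "Inspired oxygen fraction, %, at time of PaO_2 or (if no PaO_2 is known) SpO_2". No clock time of measurement is listed for any of them.
- **Other day-0 severity items.** "Arterial or venous lactate, if measured" is entered as the highest and lowest value. SOFA has no stated window. RASS is limited to the period after intubation.
- **ICU admission (list A).** ICU admission and start of ventilation are dates. The only laboratory value is the lowest creatinine of the past year, and there are no vital signs.
- **Exposure.** Day-0 fluids are listed by type and volume, without times. Vasopressor start is given in hours from ICU admission, on day 0 or, if later, on day 1 or 2. List E asks whether vasopressors were already running before ICU admission.
- **Use.** Section 3.2 hypothesises that "certain aspects of fluid and vasopressor therapy have an independent association with clinical outcomes". Section 5.5 bases the sample size on logistic regression of mortality with a small set of confounders, which it does not name.

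**The concern.** A fixed hour is a sensible rule for a full day in the ICU. Day 0 is different: it is the day on which the patient is intubated, and often also admitted, at an unpredictable hour. A reading at a convenient hour may fall before ICU admission, between admission and intubation, or many hours into treatment. A MAP taken after a vasopressor has started partly reflects the vasopressor. Haemoglobin and albumin taken after large volumes are partly diluted.

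A model that claims an independent association needs severity as it stood before the treatment decision. If the same field means pre-treatment severity in one patient and treated physiology in another, adjustment for it corrects for indication in the first and only partly in the second. It may also absorb some of the effect under study. The protocol asks for the balance of fluids at an hour convenient to each centre (Section 6.2). If the physiology hour is chosen in the same way, the mix also varies by site.

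**Working it through.** **1. The plan's own figures.** Section 5.5: 150 events / (0.20 ARDS incidence × 0.30 mortality) = 2500 patients; 2500 / (50 admissions × 0.25) = 200 ICUs. Both reproduce. At 10 events per variable, 150 events allow 15 model terms. These figures are not in dispute. They show that the confounder-adjusted mortality model is the analysis on which the study size rests.

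**2. Can the order be reconstructed from the listed fields?**

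| Event | What is recorded | Clock time available? |
|---|---|---|
| ICU admission | date | no |
| Start of ventilation | date | no |
| Day-0 physiology | value at a fixed hour | no |
| Day-0 fluids | type and volume | no |
| Vasopressor start | hours from ICU admission | only if the admission time were known |

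The one timed item, vasopressor start, counts from an origin that has only a date. An analysis plan can choose covariates, but it cannot recover times that were never collected.

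**3. Who is affected?** Patients ventilated at ICU admission have no days -3 to -1, and list A holds no acute physiology, so the day-0 values are their earliest. Patients intubated later also have list D values from the preceding days, although treatment may already be running then.

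**4. Which exposures are affected?** A day-0 value precedes all day 1 and day 2 fluid volumes, and any vasopressor first started after day 0. The lost order concerns only vasopressors and fluids given on or before day 0.

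**5. Illustration of how far the reading hour matters.** These are assumptions, not protocol figures. Let the intubation hour T be uniform on 0 to 24.
- 06:00 reading precedes intubation: P(T > 6) = 18/24 = 75%.
- 12:00 reading: 12/24 = 50% on each side.
- 22:00 reading follows intubation: P(T < 22) = 22/24 = 92%, with a mean lag of 22/2 = 11 h.

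If instead 70% of intubations fall evenly between 08:00 and 20:00 and 30% evenly over the other 12 hours, a 06:00 reading follows intubation in 6 × 0.30/12 = 15%. An 18:00 reading follows it in 8 × 0.30/12 + 10 × 0.70/12 = 78%.

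**6. Illustration of the mechanism.** In a simulation of 400,000 patients, the exposure has no effect on death. Severity raises exposure (log-OR 1.0 per SD) and death (log-OR 0.8 per SD), and exposure raises MAP by 1 SD. The MAP-adjusted OR for exposure is:

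| Share of MAP values taken after exposure | Adjusted OR |
|---|---|
| 0% | 0.99 |
| 25% | 1.24 |
| 50% | 1.49 |
| 75% | 1.78 |
| 100% | 2.21 |

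All coefficients are assumed, and MAP before exposure is taken to capture severity perfectly, which makes the contrast sharp. The shares here are after exposure, not after intubation, so steps 5 and 6 must not be chained.

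**The case against.** The strongest reply has five parts.

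- **The role of these variables is not stated.** Section 5.5 names no confounders, Section 6.2 uses the word baseline for ICU-admission data, and Section 8.2 leaves each analysis to its own plan. This stands: the point is conditional on these values being used for adjustment, and the choice of adjusters is rightly left open.
- **Intubation is not the start of exposure.** Vasopressors may begin before ICU admission, on day 0 or later. This stands. A reader might infer from the 75% and 92% that the field is pre-treatment in most patients at one site and post-treatment in most at another. The documents do not support that: the percentages concern intubation under assumed reading hours.
- **Nothing links the reading hour to country income.** This stands too. A reader might infer that the LMIC versus HIC comparison is biased, but no passage suggests that the hour differs between the two groups.
- **SOFA is also collected on day 0.** True, but its window is not given, and lactate covers the highest and lowest of the day, so neither restores the order.
- **A routine hour saves work across at least 200 ICUs.** This is a fair reason to keep it on full ICU days. It is weaker for the one day that straddles intubation, where the protocol itself already anchors RASS.

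It is also fair that the last value before ventilation need not precede vasopressors, and that a pre-intubation PaO2 would sit badly with the day-0 imaging and cardiac-failure items, which appear to serve ARDS identification. Both bear on the remedy, not on the defect.

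**Conclusion.** The point holds in a limited form. The day-0 sampling rule is unrelated to ICU admission, ventilation or treatment, and the listed fields do not allow the order to be rebuilt afterwards. For patients ventilated at ICU admission, adjustment using these values would control for indication unevenly between patients and, if the hour differs by site, between sites.

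The size of the bias cannot be derived from the protocol. It depends on the hours chosen, the timing of intubation and treatment, and which covariates are eventually used. The illustrations above show only that the reading hour can shift the before/after mix widely and that such a mix can produce an association where there is none.

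The descriptive primary aim, day 1 and 2 fluid exposure, and vasopressors first started after day 0 are untouched by this ordering problem. The change is worth making before data collection because the missing times cannot be supplied by a later analysis plan. It is not a flaw that undermines the study as a whole.

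**What to change.** For day 0 only, replace the fixed time point in list B with the value closest to the start of invasive ventilation:

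- MAP, heart rate, haemoglobin, albumin and creatinine: prefer the last value before ventilation starts.
- PaO2 (or SpO2) with FiO2: take the first value after ventilation starts, so that it still serves ARDS identification.

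Record the clock time of each of these values, and of ICU admission and ventilation start. Together with the existing hours-to-vasopressor item and the question on vasopressors before ICU admission, values taken in the ICU can then be classed as before or after vasopressor start. Day-0 fluids would remain untimed, so their order relative to the values would not be fully recovered.

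Keep the fixed time point on all other days, and leave the choice of adjustment set to the SAP.

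Cost: a few extra time fields in the eCRF and a slightly longer chart look-up for one day per patient.

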5.5. Sample size calculation

No formal sample size calculation is necessary for the primary endpoint. However, for investigating associations of aspects of fluid and vasopressor therapy with mortality using logistic regression and adjusting for a limited set of pre-specified confounders, we estimate to need 150 ‘events’ using the 10 event per variable rule of thumb. As fluid and vasopressor management is particularly important in patients with acute respiratory distress (ARDS), we will need at least 150 events in this subgroup. With an incidence of ARDS of approximately 20% and a mortality rate of 30%, we estimate to need 2500 patients to have 150 events in patients with ARDS (37). Assuming that a participating ICU has 50 unique admissions in 4 weeks on average, of which 25% is invasively ventilated for > 24 hours, we expect to need a minimum of 200 participating ICUs (38-40).

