6.1.2. Secondary study parameters

- Time of start of vasopressors;
- Route of administration for vasopressors (i.e. central vs. peripheral route);
- Types of vasopressor used;
- Daily urine output;
- Cumulative fluid balance;
- Timing of start, type and infusion time (i.e. bolus vs. continuous infusion) of administered diuretic;
- Incidence of atrial arrhythmias;
- Incidence of acute respiratory distress syndrome (ARDS)
- Incidence of renal replacement therapy;
- Incidence of persistent renal dysfunction, defined as the need for renal replacement therapy at ICU discharge;
- ICU length of stay, defined as the time between ICU admission and discharge or death;
- Hospital length of stay, defined as the time between hospital admission and discharge or death;
- Duration of ventilation, defined as the time between initiation of invasive ventilation and successful liberation of ventilation.
- Ventilator-free days and alive at day 28, defined as 28 - x if successfully liberated from ventilation x days after initiation. If subject dies within 28 days ventilator-free days is set to 0;
- All-cause ICU mortality, defined as any death during ICU stay;
- All-cause in-hospital mortality at day 28, defined as any death during hospital stay before or on study day 28;
- All-cause in-hospital mortality at day 60, defined as any death during hospital stay before or on study day 60;
- All-cause in-hospital mortality at day 90, defined as any death during hospital stay before or on study day 90;

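### On days 0 to 2 the bilateral-opacities item cannot separate no chest imaging from no opacities and appears to depend on a yes to respiratory symptoms, so recorded ARDS may be biased

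*Protocol*

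**What the plan says.** Section 6.2.3 of the protocol lists the daily data. List B (day 0) and list C (days 1 and 2) each contain the onset question "Was there new-onset (<7 days) respiratory symptoms, or acute worsening of respiratory symptoms?, yes/no, if yes", followed directly by "Are there bilateral opacities on chest imaging (including lung ultrasound), yes/no" and then by a question on whether cardiac failure explains any hypoxemia. The opacity item has two answers only.

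Other items in the same section do provide for a missing measurement. On day 0 the list has "Arterial or venous lactate, if measured", with similar wording for venous oxygen saturation, and SpO2 stands in when PaO2 is not known.

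The onset and opacity items are absent from list D (days 3 to 7 and the days before intubation). List E (events) asks whether acute kidney injury or rhabdomyolysis developed, but not ARDS. List F (follow-up) has no ARDS item either.

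Three parts of the protocol use ARDS status:
- Section 6.1.2 makes ARDS incidence a secondary parameter.
- Section 8.2 defines a subgroup by an ARDS diagnosis in the first three calendar days of ICU admission.
- Section 5.5 builds the sample size on that subgroup: "we will need at least 150 events in this subgroup".

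**The concern.** The opacity item supplies the imaging component of ARDS, and it has two weaknesses as listed.

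1. **No answer for a day without imaging.** The local investigator must enter *no* or leave the item blank. A *no* then mixes clear imaging with absent imaging. A blank mixes absent imaging with an item that was skipped or forgotten.
2. **Apparent dependence on the symptom question.** If the conditional governs the opacity item, a patient with no recorded new or worsening symptoms is never asked about imaging that day.

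A SAP can decide how to treat a blank. It cannot recover an answer that was never requested, or split a *no* into its two meanings. That makes this a matter of data capture, to be settled before data entry.

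At stake are a secondary outcome and membership of the subgroup that sets the sample size. Comparing fluid and vasopressor therapy between low- and middle-income and high-income countries is a stated aim (section 3.1), and section 2.4 describes resource differences between ICUs. If imaging frequency also differs by resources, which the protocol does not say, ARDS would be recorded less completely in one income group than in the other.

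**Working it through.** **Inputs from section 5.5.** 150 events required, set "using the 10 event per variable rule of thumb"; ARDS incidence about 20%; mortality 30%; 50 admissions per ICU in four weeks, of which 25% are ventilated for more than 24 hours; 200 ICUs.

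**Reproducing the plan's figures.**
- Patients: 150 / (0.20 × 0.30) = 2500, which agrees with "we estimate to need 2500 patients to have 150 events in patients with ARDS".
- ICUs: 50 × 0.25 = 12.5 patients per ICU, and 2500 / 12.5 = 200.
- Model size implied by the rule: 150 / 10 = 15 parameters.

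The figures are correct. They leave no margin at the stated minimum, because 200 × 12.5 = 2500 exactly.

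**Sensitivity to missed cases.** Let m be the share of true ARDS cases that the form fails to record. The protocol gives nothing from which to estimate m, so the values below are assumptions. Missed cases are first given the same 30% mortality.

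- Recorded incidence = 0.20 × (1 − m)
- Recorded ARDS deaths = 2500 × 0.20 × (1 − m) × 0.30 = 150 × (1 − m)
- Patients needed for 150 recorded deaths = 2500 / (1 − m), and ICUs = that number / 12.5, both rounded up

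| m (assumed) | Recorded incidence | ARDS deaths at 2500 | Deaths per parameter (15) | Patients for 150 deaths | ICUs |
|---|---|---|---|---|---|
| 0% | 20% | 150 | 10 | 2500 | 200 |
| 5% | 19% | 142.5 | 9.5 | 2632 | 211 |
| 10% | 18% | 135 | 9 | 2778 | 223 |
| 20% | 16% | 120 | 8 | 3125 | 250 |

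If missed cases have a mortality of 20% to 40% instead of 30%, the deaths kept are 150 − 500 × m × mortality. That gives 140 to 130 at m = 10%, and 130 to 110 at m = 20%.

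**Direction.** A true case entered as *no* for want of imaging, or stopped at the symptom question, is lost; neither feature produces a false positive. The downward direction does depend on coding. If unimaged patients were instead left blank and dropped from the denominator, incidence would be estimated in imaged patients only. That could err either way, although unimaged patients would still not enter the subgroup.

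**The case against.** Several counter-arguments have force.

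- **The dependence is inferred.** The list in the available text does not show reliably which items are nested. The conditional wording would have no function if nothing followed from it, and the same construction introduces dependent items for renal replacement therapy and vasopressors. But the nesting is likely, not certain. This stands as a reason to say *appears*. The missing third answer does not depend on it.
- **Section 6.2.3 lists variables and is not the form.** The eCRF is not shown and may already hold a further option, and classifying missing components is ordinary SAP content. It follows that the protocol does not make unimaged patients ARDS-negative. A reader might infer such a default, but no section states one. What remains is that the list, if followed, does not capture the distinction.
- **Provision for missing values is not general in the list.** Creatinine, hemoglobin and albumin on these days carry none. That weakens the contrast with lactate. However, a blank laboratory value cannot be mistaken for a result, whereas a *no* for opacities can.
- **There are three chances to record opacities.** Lung ultrasound counts as imaging, and one positive day would naturally suffice. This limits the loss but does not remove it.
- **The symptom question may be a deliberate onset criterion.** Data come from the chart (section 6.2.2), so a history from before intubation is available. A reader might infer that sedated patients must be answered *no*; nothing in the protocol supports that. There is no case here for rewording the onset criterion.
- **The size is not in the document.** The 20% incidence comes from a cited study and may already reflect routine under-recording, in which case the reductions shown would be too large. The protocol's comparison by income group also names fluid and vasopressor therapy, not ARDS incidence, so a false ARDS difference between income groups is a possibility and not a demonstrated result.

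**Conclusion.** The point holds as a weakness in data capture. As listed, the day 0 to 2 items cannot separate absent imaging from absent opacities, they may leave the imaging question unasked in patients without recorded symptoms, and no later item makes up for it. Recorded ARDS incidence and subgroup membership may be biased. The bias is probably downward if unimaged patients are entered as *no*, and uneven between income groups if imaging frequency differs. Both conditions are assumptions.

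The size cannot be determined from the protocol; the reductions shown above are illustrations only. A reader might go further and infer that the 150-event figure is understated or that the sample size is miscalculated. It is not: 150, 2500 and 200 reproduce exactly, 200 ICUs is a stated minimum, and only the number of events achieved could fall short. This is a cheap improvement worth making, not a sample-size error.

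**What to change.** On days 0, 1 and 2:

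1. Ask the opacity item of every patient, with three answers: yes, no, no chest imaging that day.
2. Keep the symptom and onset item as a separate question with its present wording, so that it can still serve as a timing criterion in the analysis.
3. State that a patient with no chest imaging on any of these days has ARDS status unknown, not negative, and report the share of such patients by income group.

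The cost is one extra answer option, one more item for patients now skipped, and a small group reported with unknown ARDS status. The stated sample size does not change. The first two changes need to be in the eCRF before data entry starts, because they cannot be made good at analysis. If the eCRF already has these features, aligning section 6.2.3 with it is enough.
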